Title: Using Combined EEG and Non-invasive Brain Stimulation to Examine and Improve Reward Functioning in Opioid Use Disorder

NCT number: NCT04432493

Date: 12/04/2018

Statistical analysis. First, we predict that people with OUD will exhibit a truncated reward positivity elicited by monetary rewards, compared to healthy controls. This finding would indicate that OUD individuals are impaired at using normal rewards to develop internal representations of action value, and thus are impaired at using these action values for cognitive control. Second, we predict that repetitive TMS will lead to increases in dopamine release and neuronal activity in the ACC, thereby leading to a positive shift in the ACC valuation of monetary rewards in OUD as revealed by an increase in reward positivity amplitude in the active TMS group relative to the sham group. To test these predictions, we will conduct a 2×2 repeated measures analysis of variance with TMS (active vs sham) and Group (OUD vs. controls) as factors.

We anticipate the following results:

- *Aim 1:* A Group (OUD, control) by TMS (active, sham) interaction, where OUD participants in the sham condition will demonstrate an attenuated reward positivity signal relative to the control participants in the sham condition.
- *Aim 2:* A within-group main effect of TMS (active, sham) where participants receiving active TMS will demonstrate a larger reward positivity compared to participants in the sham condition. We also anticipate a 2-way TMS (active, sham) by Group (OUD, control) interaction, where control participants receiving the active TMS will demonstrate a larger reward positivity signal relative to the SHAM control group. We also anticipate OUD participants receiving active TMS will demonstrate a larger reward positivity relative to OUD SHAM.

Linear regression models will be used to compare groups while adjusting for potential confounds within each age group and for the whole sample while controlling for age and education. Post hoc analysis (e.g., Tukey HSD) will be performed when linear regression shows any significant main effects or interactions. In all comparisons, sex will be considered as a biological variable to assess trends to be explored further in the R01 longitudinal study.

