4.1. Study Design

4.1.a. Detailed Description

Thirty opioid dependent and 30 healthy control participants will be recruited for the purposes of this study. Participants in each group will be randomized into either TMS or sham conditions (15 participants per group). Standard practice in electrophysiological studies commonly use a minimum of 15 participants per experimental group. All participants will complete consent protocols, and questionnaires regarding demographic and drug use history, and will be fitted with an EEG cap for ERP recording while they engage in a virtual T-maze choice task. A neuronavigation robot will position the TMS coil over a predetermined area of the brain, and TMS pulses will be delivered at 110% of the participants resting motor threshold at 10 Hz continuously over the predefined DLFPC target immediately before each of the 20 blocks of 10 trials, for a total of 1000 pulses and 200 trials (fixed at 100 reward and 100 no-reward). Identical parameters will be applied to the SHAM group with the exception that the TMS coil will be flipped 180° to mimic auditory stimulation.

4.1.b. Primary Purpose

Basic Science

4.1.c. Interventions

Type	Name	Description
Device (including sham)	TMS	Participants will be randomized into either the TMS (active) or SHAM group (coil flipped 180° to mimic auditory stimulation) during task performance. The TMS stimulator device used on our laboratory is a MagPro X100 with the Cool-B70 figure-of-eight coil (MagVenture, Falun, Denmark). The selection of stimulation intensity will be based on Resting Motor Threshold (rMT). In keeping within the safety guidelines, stimulation intensity will be set as 110% of rMT for the repetitive TMS. 50 rTMS pulses will be delivered at 110% of participants' resting motor threshold at 10 Hz continuously over the predefined DLFPC target immediately before each of the 20 blocks of 10 trials, for a total of 1000 pulses and 200 trials (fixed at 100 reward and 100 no-reward). Identical parameters will be applied to the SHAM group with the exception that the TMS coil will be flipped 180° to mimic auditory stimulation.

4.1.d. Study Phase

Early Phase 1 (or Phase 0)

Is this an NIH-defined Phase III Clinical Trial? Yes No

4.1.e. Intervention Model

Parallel

4.1.f. Masking

Yes No

Participant Care Provider Investigator Outcomes Assessor

4.1.g. Allocation

Randomized

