4.6. Is this an applicable clinical trial under FDAAA? (SEE SECTION 6.6)

4.7. Dissemination Plan

[Dissemination_R21_opioid.pdf](#)

Statistical design and power

This study will adopt a randomized sham-controlled design. Participants will be randomized into either the TMS (active) or SHAM group (coil flipped 180° to mimic auditory stimulation) during task performance. Thirty dependent opioid users (OUD group) and 30 controls with no history of alcohol or drug dependence will be recruited for this study (15 participants per TMS/sham group). Standard practice in electrophysiological studies commonly use a minimum of 15 participants per experimental group. Further, based on previous work [27-29] an estimated 60 subjects in total will be required to identify a moderate to large main effect on the reward positivity, critical $F(4, 55) = 4.01, p = 0.05, 85\%$ power.

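### Aim 1 is labelled a Group by TMS interaction, but the result it describes is a sham-arm difference, which the interaction does not test

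*SAP*

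**What the plan says.** The SAP opens its statistical section with an unrestricted group comparison: "we predict that people with OUD will exhibit a truncated reward positivity elicited by monetary rewards, compared to healthy controls". It then assigns one 2×2 analysis of variance, TMS by Group, to all predictions, and lists anticipated results by aim.

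- **Aim 1** expects "A Group (OUD, control) by TMS (active, sham) interaction, where OUD participants in the sham condition will demonstrate an attenuated reward positivity signal", the comparator being controls who receive sham.
- **Aim 2** expects "A within-group main effect of TMS (active, sham) where participants receiving active TMS will demonstrate a larger reward positivity". The same interaction is then named again: "We also anticipate a 2-way TMS (active, sham) by Group (OUD, control) interaction, where control participants receiving the active TMS" exceed their sham counterparts. Finally, "OUD participants receiving active TMS will demonstrate a larger reward positivity relative to OUD SHAM".

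A regression follows: "Linear regression models will be used to compare groups while adjusting for potential confounds within each age group". Post hoc comparisons, with Tukey's procedure given as an example, are to be run once that regression shows a significant term of any kind.

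The protocol (4.1.a, Detailed Description) randomizes each group to active or sham, giving four separate cells of 15. Its Statistical design and power section says that "an estimated 60 subjects in total will be required to identify a moderate to large main effect on the reward positivity", with 85% power.

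**The concern.** Aim 1 carries the name of one test and the description of another, and the opening prediction suggests a third:

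1. the Group by TMS interaction (the label);
2. OUD-sham against control-sham (the result described);
3. the Group main effect, which averages over active and sham (the opening prediction).

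These are different quantities. If TMS lifts both groups equally, a real sham deficit sits beside an interaction of exactly zero. If TMS lifts only controls, there is an interaction with no sham deficit. An analyst who follows the label may therefore report Aim 1 as unsupported when the deficit it describes is present. Because no deciding test is named, the choice among the three stays open after the data are seen.

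**Working it through.** **Inputs.** 15 participants in each of four cells (protocol 4.1.a), all between-participant, so error df = 60 − 4 = 56 and the two-sided 5% critical t is 2.003. The deficit and the lifts are assumed, because the documents give no effect size.

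**The plan's own figure.** The 85% cannot be reproduced without an effect size, but it can be inverted. The printed critical value 4.01 fits a test with one numerator df (F(1,56) = 4.013) and not the printed F(4,55), whose critical value is 2.54. Taking a 1-df main effect at N = 60, 85% power needs f = 0.394, that is d = 2f = 0.787. The upper bound of 1.09 comes from the Recruitment and Retention Plan (n = 15, power .82), if that means a two-sample comparison with 15 per group. The lower bound of 0.5 is an assumption.

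**Formulas (SD units).** Let d be the sham deficit, Lo the OUD lift and Lc the control lift.

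- Sham contrast: estimate d, SE √(2/15) = 0.365.
- Interaction: estimate Lo − Lc, SE √(4/15) = 0.516.
- Group main effect: estimate d − (Lo − Lc)/2, SE √(1/15) = 0.258.

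Power is from the noncentral t with noncentrality equal to estimate/SE.

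**At d = 0.787.**

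- Group main effect with equal lifts: 0.787/0.258 = 3.05, power 85% (recovers the input).
- Sham contrast: 0.787/0.365 = 2.16, power 56%, whatever the lifts.
- Interaction, OUD lifted by d and controls by d/2: 0.394/0.516 = 0.76, power 12%.
- Interaction, OUD only lifted by d: 0.787/0.516 = 1.52, power 32%.
- Tukey on the sham pair: critical t 2.648 with the same noncentrality of 2.16, power 32%.

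The last two columns below are from simulation, 2,000,000 trials per pattern, counting the sham contrast only in the predicted direction.

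| OUD lift, control lift | Interaction | Sham contrast | Group main effect | Interaction and sham deficit both significant | Interaction and sham verdicts differ |
|---|---|---|---|---|---|
| d, d | 5% | 56% | 85% | 3% | 56% |
| d, d/2 | 12% | 56% | 61% | 11% | 46% |
| d, 0 | 32% | 56% | 32% | 29% | 31% |
| 1.5d, 0.25d | 47% | 56% | 20% | 39% | 26% |
| 2d, 0.5d | 61% | 56% | 12% | 47% | 24% |
| d/2, d | 12% | 56% | 96% | 2% | 65% |

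The written route (any significant term, then the Tukey sham pair) detects the deficit in about 32% of trials in every row. The gate hardly matters; the Tukey threshold sets the figure.

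**Break-even.** The interaction has more power than the sham contrast only if |Lo − Lc|/0.516 exceeds d/0.365, that is if the lifts differ by more than √2·d = 1.41d. If OUD has the larger lift, the active-arm difference is then −d + 1.41d = +0.41d or more, so OUD-active must exceed control-active. If controls have the larger lift, the active-arm gap must exceed d + 1.41d = 2.41d.

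**Range over d = 0.5 to 1.09.** Sham contrast 27% to 83%; interaction with half lift 8% to 18%; interaction with OUD-only lift 16% to 54%.

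**The case against.** The best defence is that Aim 1 means a significant interaction followed by a comparison of the sham cells, and that the SAP provides for that comparison through its post hoc rule. Part of this stands. A four-cell Tukey analysis does include OUD-sham against control-sham, so it would be too strong to infer that the plan offers no route to the sham comparison. But Tukey is only an example, the rule is triggered by any significant regression term, and nothing ties it to Aim 1. Read this way, the route has about 32% power. A strict reading that requires both the interaction and the sham deficit has about 3% to 29% in the first three patterns.

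A reader might also infer that an interaction without a sham deficit would be counted as success. The wording does not support that. It asks for an interaction in which the sham deficit appears. With no deficit and only controls lifted by d, a significant interaction together with a significant sham deficit occurred in about 0.04% of simulated trials. A control-only lift also conflicts with Aim 2, which expects a lift in OUD.

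Two further readings fail. The opening prediction is not left untested, because the Group main effect addresses it. Aim 2 does not contradict itself, because unequal lifts in both groups produce an interaction; the SAP only omits which lift is expected to be larger.

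Finally, this is an Early Phase 1 basic-science study and the aims are written as anticipated results. That limits the stakes, but a list of expected patterns still leaves the deciding test unnamed.

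**Conclusion.** The point stands as a mismatch between label and described result, with no stated rule for deciding Aim 1. The logical part needs no assumed numbers: the interaction is neither necessary nor sufficient for the sham-arm deficit. Its practical size depends on the assumed deficit and lifts. At d = 0.787, the interaction and sham-contrast verdicts differ in about 24% to 65% of trials over the six patterns considered. The interaction is the more powerful test in only one of the six, where OUD-active exceeds control-active. The value 0.787 rests on reading the protocol's power statement as a 1-df main effect. The figures ignore covariate adjustment and dropout. They do not show that the sham contrast is well powered; they show that it is the test that matches the claim.

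**What to change.** In the 2×2 between-subjects model, name control-sham minus OUD-sham (pooled error, two-sided 0.05) as the planned test of Aim 1. State that it is not conditional on the interaction or on the post hoc Tukey rule, and remove the interaction as Aim 1's test. If the contrast is read from the regression, state that sham is the reference level, so that the Group coefficient is this contrast. Report the Group by TMS interaction as a separate estimate with a 95% confidence interval. If the opening prediction is kept as a separate claim, say that the Group main effect tests it.

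The cost is SAP wording only, with no change to data, visits or sample size. The downside is power below the 85% stated for a main effect: 56% at d = 0.787, with 80% needing d of about 1.04. The SAP should say so. The confidence intervals will be wide, with half-widths of 2.003 × 0.365 = 0.73 SD for the sham contrast and 2.003 × 0.516 = 1.03 SD for the interaction.

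### Aim 2 makes a claim about OUD but does not name the OUD active-versus-sham contrast as its deciding test, and leaves that contrast to gated post hoc testing

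*SAP*

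**What the plan says.** The target is stated for the patient group. In the SAP's opening paragraph, the second prediction is "a positive shift in the ACC valuation of monetary rewards in OUD as revealed by an increase in reward positivity amplitude", comparing active with sham. The SAP title is likewise about reward functioning in OUD.

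The test named for both predictions is general: "we will conduct a 2×2 repeated measures analysis of variance with TMS (active vs sham) and Group (OUD vs. controls) as factors". Half of the planned 60 participants are healthy controls, and the Protocol (Statistical design and power) gives "15 participants per TMS/sham group", so there are four cells of 15.

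Under Aim 2 the SAP anticipates, in this order:

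1. "A within-group main effect of TMS (active, sham) where participants receiving active TMS will demonstrate a larger reward positivity" than those receiving sham.
2. A TMS-by-Group interaction, "where control participants receiving the active TMS will demonstrate a larger reward positivity signal relative to the SHAM control group".
3. "We also anticipate OUD participants receiving active TMS will demonstrate a larger reward positivity relative to OUD SHAM".

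The SAP does not say which of these decides Aim 2. The only route it gives to a comparison of individual cells is "Post hoc analysis (e.g., Tukey HSD) will be performed when linear regression shows any significant main effects or interactions".

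**The concern.** Only the third result speaks directly to the prediction. The main effect is the mean of the lift in OUD and the lift in controls, so controls alone can produce it. The second result is described by a simple effect in controls, which is not an interaction pattern. The third has the same sign, so the text never says which group should gain more. An interaction in which TMS helps controls and not OUD would fit that sentence as it stands.

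Two things are at stake. A significant pooled result or interaction could be reported as meeting Aim 2 when OUD participants did not respond. Conversely, if TMS works only in OUD, the pooled test dilutes the effect, and the contrast that would show it must pass a gate and then a multiplicity penalty designed for all pairs of cells.

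**Working it through.** **Inputs from the documents.** Four cells of 15, total 60, parallel randomised groups, alpha 0.05, 85% power for a main effect, critical F printed as 4.01 (Protocol 4.1 and Statistical design and power). Both factors are treated as between-participant. No numeric effect size is given.

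**The plan's own figure.** A critical F of 4.01 belongs to one numerator degree of freedom: F(1, 56) = 4.013. The printed degrees of freedom (4, 55) would give 2.54; that mismatch is a separate matter. With one numerator df and N = 60, 85% power needs f = 0.394, that is d = 2 × 0.394 = 0.79. So d = 0.79 is back-calculated and does not appear in the documents.

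**Assumptions.** Within-cell SD 1, pooled error on 56 df, two-sided 5% (critical t = 2.003). The main effect and OUD contrast count only when active exceeds sham; the interaction counts in either direction. The post hoc gate is taken as a significant main effect or interaction in the 2×2 model, and Tukey as all pairs of four cells (critical t = q/√2 = 2.648).

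**Formulas.**
- Main effect: (lift in controls + lift in OUD)/2, with SE = √(1/30 + 1/30) = 0.258.
- Interaction: (lift in OUD − lift in controls)/2, with the same SE.
- OUD contrast: lift in OUD, with SE = √(2/15) = 0.365.

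**TMS effect in controls only (OUD lift = 0).** The noncentrality of the main effect is (d/2)/0.258: 0.968, 1.549 and 1.936 for d = 0.5, 0.8 and 1.0. That of the interaction has the same size. The OUD contrast has noncentrality 0. The either-result row comes from simulation; the others are noncentral t and agree with the simulation.

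| Significant result | d = 0.5 | d = 0.8 | d = 1.0 |
|---|---|---|---|
| Main effect, active > sham | 16% | 33% | 48% |
| Interaction | 16% | 33% | 48% |
| Main effect or interaction | 29% | 55% | 72% |
| OUD active > sham, planned | 2.5% | 2.5% | 2.5% |
| OUD active > sham, Tukey | 0.5% | 0.5% | 0.5% |

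The interaction is then almost always in the direction of a larger effect in controls.

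**TMS effect in OUD only.** At d = 0.79, the main effect has noncentrality 0.395/0.258 = 1.53 and the OUD contrast 0.79/0.365 = 2.16.

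| Test | d = 0.5 | d = 0.79 | d = 1.0 |
|---|---|---|---|
| Pooled main effect | 16% | 32% | 48% |
| OUD contrast, Tukey after the gate | 11% | 32% | 54% |
| OUD contrast, planned | 27% | 57% | 77% |

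The planned contrast at d = 0.79 is 56.6% with the pooled error.

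**Equal effect in both groups, d = 0.79.** Main effect 85% (noncentrality 0.79/0.258 = 3.06), planned OUD contrast 57%, interaction 5%. Equal lifts therefore give no interaction beyond chance, although the SAP anticipates lifts in both groups and an interaction without saying how the lifts differ.

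**The case against.** The strongest reply is that the SAP contains no rule accepting a control effect. A reader might infer that any one Aim 2 result suffices, or that a response in controls alone would confirm the OUD claim. The documents do not support that: the SAP only lists what it anticipates, defines neither support nor confirmation, and does include the OUD active-versus-sham result. Read as a joint pattern, Aim 2 would almost never be met by a controls-only effect, since the OUD result would appear in about 2.5% of such trials. This stands, and it makes the defect a missing decision rule.

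For the same reason, larger figures should not be used. Counting any of four findings (main effect, interaction, and each simple effect) gives 81% at d = 1.0 in controls only, but that treats the control contrast as evidence about OUD, which the SAP nowhere does. The matching 13% when TMS has no effect at all counts results in the wrong direction; it is 9% with the main and simple effects restricted to increases.

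A pooled effect is also a legitimate question here. The Protocol gives the primary purpose as basic science (4.1.b), defines the primary outcome without restriction to OUD (4.2), and sizes the trial for a main effect. That justifies reporting the main effect; it does not turn it into evidence about OUD. Finally, the term within-group might mean separately within each group. The main effect of the stated 2×2 model is pooled, so if the other meaning was intended the SAP needs to say so.

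**Conclusion.** The concern holds as a gap between the claim and its test. The prediction is about OUD. The main effect mixes OUD with healthy controls, the interaction has no stated between-group direction, and the one contrast that answers the question is neither named as decisive nor tested in its own right. With a controls-only effect of 0.5 to 1.0 SD, a significant main effect or interaction arises in 29% to 72% of trials, against 2.5% for the OUD contrast. With an OUD-only effect of 0.79 SD, a planned contrast has about 57% power, against about 32% by either existing route.

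These figures rest on assumed effect sizes, equal variances, full cells of 15, and the gate and Tukey procedure as specified above; the SAP offers Tukey only as an example. The direction of the conclusion does not depend on the particular d. Severity: should-fix. All four cells are analysed and the OUD result is anticipated, so what needs repair is the rule for inference; the data collected are adequate to apply it.

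**What to change.** Amend Aim 2 in the SAP, before outcomes are analysed by allocation, to say:

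- The claim that TMS raises reward positivity in OUD rests on one pre-specified contrast, OUD-active minus OUD-sham, reported as an estimate with 95% CI and tested at two-sided 5% using the pooled error of the 2×2 model. It is tested whatever the ANOVA or regression shows and is exempt from the post hoc rule.
- The TMS main effect is reported as the average over OUD and healthy participants, and does not by itself support the OUD claim.
- The interaction is defined as the OUD lift minus the control lift, with its CI, and supports a larger benefit in OUD only if positive.

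Exempting the contrast matters: naming it but leaving it behind the gate and Tukey would keep power near 32% at d = 0.79.

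The cost is SAP wording, with no new participants or data. The downside is that if both groups respond equally at d = 0.79, the OUD claim has about 57% power, against 85% for the pooled test. The pooled test is still reported. The limit of 15 versus 15 is already in the design, and the change makes it visible.

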Inclusion of Children: Previously, NIH considered individuals under 21 years of age to be children, but this has now changed (children are now defined as under 18; see NIH NOT-OD-16-010). We will be including 18- 55 year olds in our study. Thus, we will not be including children in this project. Note that the investigators have had ample previous experience working with participants in this age range (e.g., those 18-20 years old), and all study procedures are appropriate for this age range. Children below age 18 will not be studied in this project because a separate age-specific project is warranted, and even preferred, given that normal developmental changes in cognitive control processes during childhood are prominent, but not yet well understood.

Recruitment and Retention Plan

In total, we plan to collect 60 participants (30 opioid users, 30 controls) over 2 years for the proposed study. Participants will be randomized into TMS or sham groups (15 participants per group). Standard practice in electrophysiological studies commonly use a minimum of 15 participants per experimental group. Further, basing the analyses on our previous results, a priori power analysis indicated that a sample size of 15 would be sufficient to detect a significant effect with a power of .82 and an alpha of .05. Potential OUD participants will be recruited through the community using an 'expression of interest' flyer. The flyer will be distributed throughout pharmacies, clinics, universities, community recreation venues, via email, social networking websites and possibly through media outlets such as through newspapers and radio. Control participants will be recruited using personal networks, advertisements on volunteer job sites and by placing flyers in local community settings.

TIMELINE

Months 1–18. Aim 1 and Aim 2 (initiation) Recruiting and testing control and OUD subjects with our virtual T-maze task with Ri-TMS capabilities, which is already developed.

Months 18–24. Completion of Aim 1 and Aim 2. Analyse data from Months 1–18 for publication. Prepare and submit manuscript for publication.

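### Three cell contrasts are predicted in advance but have no planned test: the only pairwise route is gated and post hoc, and with Tukey as the example it gives up about 5 to 17 points of power compared with Holm over the three

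*SAP*

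**What the plan says.** The SAP (Statistical analysis) assigns its predictions to one model: "we will conduct a 2×2 repeated measures analysis of variance with TMS (active vs sham) and Group (OUD vs. controls) as factors". Under Aims 1 and 2 it then states three directional differences between cells.

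- Aim 1: "OUD participants in the sham condition will demonstrate an attenuated reward positivity signal relative to the control participants in the sham condition".
- Aim 2, controls: active TMS gives a larger reward positivity than sham.
- Aim 2, OUD: "We also anticipate OUD participants receiving active TMS will demonstrate a larger reward positivity relative to OUD SHAM".

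The last paragraph introduces linear regression adjusted for age and education and adds: "Post hoc analysis (e.g., Tukey HSD) will be performed when linear regression shows any significant main effects or interactions". No other sentence says how two cells are to be compared.

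On size, Protocol section 4.1.a says "Participants in each group will be randomized into either TMS or sham conditions (15 participants per group", so each predicted contrast is 15 v 15. The Protocol gives two power statements. The Recruitment and Retention Plan says that "a sample size of 15 would be sufficient to detect a significant effect with a power of .82 and an alpha of .05". Statistical design and power (the attachment to section 4.3) says that "an estimated 60 subjects in total will be required to identify a moderate to large main effect on the reward positivity". Neither gives an effect size or SD, and the second concerns a main effect, not a cell contrast.

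**The concern.** A 2×2 ANOVA tests two main effects and an interaction. None of these is a simple effect. A significant interaction does not show that OUD-sham lies below control-sham, or that TMS raises the signal in OUD. If TMS helps both groups equally, there is no interaction to find. The claim that active TMS raises reward positivity in people with OUD is the OUD-active v OUD-sham contrast, and its test is left to a post hoc step.

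That step has three weaknesses.

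1. It depends on a significant term in the regression, which is not the model named to test the predictions.
2. Tukey is only an example and no family is stated, so the correction can be chosen after the data are seen.
3. If Tukey is applied to all four cells, it protects six pairs, three of which nobody predicted. The predicted contrasts pay for that protection in power.

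**Working it through.** **Inputs.** Four cells of 15 (Protocol 4.1.a), so error df = 60 − 4 = 56. Alpha is 0.05 (both power statements). Two-sided tests, equal cells, no covariates and no dropout are my assumptions.

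**The plan's own power figure.** The Protocol prints "critical $F(4, 55) = 4.01, p = 0.05, 85\%$ power". The 5% critical F is 4.013 on (1, 56) df and 4.016 on (1, 55), so 4.01 fits a one-df effect; the printed (4, 55) would give 2.54. With λ = f²N, N = 60 and df (1, 56), 85% power needs f = 0.394, so λ = 0.394² × 60 = 9.3. For a two-level factor d = 2f = 0.79. An assumed f of 0.40 gives 86.1%. The 85% is therefore consistent with a one-df main effect of d about 0.79, tested on 30 v 30.

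The other statement (power 0.82 with 15), read as 15 per group, two-sample and two-sided, implies d = 1.09 on 28 df. With the pooled 56 df, 82% corresponds to d of about 1.07.

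**Effect sizes used.** All are assumptions carried over to a cell contrast: 0.79 and 1.07 from the back-solving above, with 0.5 and 1.2 to show the range.

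**Critical values, 56 df.**

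- Unadjusted: t = 2.003.
- Tukey, 4 cells and 6 pairs: q(0.95; 4, 56)/√2 = 3.745/√2 = 2.648, a per-comparison alpha of 0.0105.
- Holm over three: the first step uses 0.05/3, t = 2.468. Later steps use 0.05/2 and then 0.05, so they are easier. Holm's strictest step is therefore below Tukey's threshold.

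**Power for one contrast.** The noncentrality is d/√(2/15) = 2.739d, which is 1.37, 2.16, 2.93 and 3.29 at the four sizes. Unadjusted and Tukey power follow from the noncentral t. The gate (any main effect or interaction significant at 5%) and Holm were simulated, with 200,000 trials per scenario. The Holm range runs from a pattern in which only OUD-sham is low to an additive pattern in which all three predicted contrasts equal d.

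| d | Unadjusted | Gate + Tukey | Holm over three | Gain, Holm over gate + Tukey |
|---|---|---|---|---|
| 0.5 | 27% | 11% | 15–16% | about 5 points |
| 0.79 | 56–57% | 32% | 41–45% | 9–13 |
| 1.07 | 82% | 61% | 71–78% | 10–17 |
| 1.2 | 90% | 73–74% | 82–88% | 9–15 |

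The range is not exhaustive. If active TMS lifts OUD participants to the level of active controls, so that the OUD effect is 2d, the contrasts of size d have 51% with Holm v 33% with Tukey at d = 0.8.

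**What the gate costs.** On top of Tukey it costs under 1 point in every scenario. Without Tukey it matters when only OUD-sham is low: power falls from 27% to about 21–22% at d = 0.5 and from about 57% to 50% at d = 0.79, a loss of about 6–7 points. Under the additive pattern at d = 0.79 or 0.8 it costs almost nothing. Replacing Tukey but keeping the gate would therefore be an incomplete repair.

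**Error control.** Holm keeps the family error at or below 5% whatever the pattern of means. Under the global null the simulated rate was about 4.5%.

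**The case against.** The strongest reply is that the SAP does not prescribe what is being criticised. Tukey appears after an e.g., no family is defined, and the sentence sits in the paragraph on adjusted regression. The predictions are assigned to the ANOVA, and the TMS main effect, the first result named under Aim 2, is tested there on 30 v 30 with no gate. An omnibus test followed by Tukey is conservative and valid, and the study is labelled Basic Science and Early Phase 1.

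Most of this stands. It rules out saying that the predicted contrasts can be reached only through Tukey, or that either aim goes untested. It does not supply a planned test of the three contrasts. An open choice of correction and family is itself a reason to fix the sentence.

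A reader might also infer that the procedure costs 20 points of power or more. That figure compares Tukey with three unadjusted 5% tests, which nobody proposes here. Even then it holds only for d between about 0.61 and 1.10: the loss is 16 points at d = 0.5 (27% v 11%) and 16 at d = 1.2 (90% v 74%). Part of the gap is the price of controlling error over the three predicted contrasts, which the fix pays too. The fair comparison is with Holm. Against plain Bonferroni over three, the gain would be only about 6–7 points at d = 0.8 to 1.1.

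**Conclusion.** The point holds as a cheap improvement. Three contrasts predicted in advance have no planned test, and the only pairwise procedure named is conditional, post hoc and not fully specified. If its example is applied to all six pairs, power per predicted contrast is lower than under Holm over the three by about 5 points at d = 0.5, 9–13 at 0.79, 10–17 at 1.07 and 9–15 at 1.2. These figures rest on assumed effect sizes, two-sided tests, full cells of 15, 56 error df and no covariates. Adding age, education and sex terms would lower the df slightly.

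The documents do not support going further. The main effects and interaction are tested directly, no inflation of false positives has been shown, and the trial's main analysis is not invalidated.

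**What to change.** Replace the post hoc sentence in the last paragraph of the SAP with:

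> The three cell contrasts named in Aims 1 and 2 (OUD-sham v control-sham; control-active v control-sham; OUD-active v OUD-sham) will be tested directly from the 2×2 between-subject ANOVA model, whether or not any omnibus effect is significant, with Holm adjustment across these three. All other cell pairs are descriptive, with 95% confidence intervals.

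This wording fixes the model, the family and the correction, and removes the gate. It says between-subject because the Protocol describes a parallel design (4.1.e) with one session per participant (4.4). The main effects and interaction stay as planned.

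The cost is SAP wording only, with no added participants or procedures. The three unpredicted pairs lose confirmatory status. The inclusion enrollment report in Protocol section 2.9 already shows 23 participants, so the change should be dated, with its reason, and made before any unblinded look at the data.
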